Administration status and (dosage administration)	
Data should be sorted by the start date of the treatment described in “Administration status of this drug” in survey sheet
 
[1] The initial administration: Patients who receive this drug at the dose of 160 mg
 
[2] The second administration: Patients who receive this drug at the dose of 80 mg
 
[3] The third administration: Patients who receive this drug at the dose of 40 mg
 
[4] The fourth or subsequent administration: Patients whose survey sheet includes a check mark in “once per 2 weeks” box and a description of 40 mg as the dose
 
*If a description of fourth or subsequent administration is found, any administration status in the fourth and subsequent administration should be described as specified in [4].
 
• If patients receive this drug four times or more, conditions [1] to [4] described above are satisfied.
 
If patients receive this drug 3 times but does not receive fourth administration, conditions [1] to [3] described above are satisfied.
 
If patients correspond to either of these 2 patterns, the dosage should be aggregated as “160mg→80mg→40mg/2 weeks, no change was made thereafter”.
 
 
• If conditions [1], [2], and [3] described above are satisfied and the dose in the fourth and subsequent administration is 160 mg or 80 mg, the dosage should be aggregated as “160mg→80mg→40mg/2 weeks, and 160 mg or 80 mg in the subsequent administration”.
 
• If [1] described above is satisfied and the second and subsequent administrations are not given, the dosage should be aggregated as “160 mg, and no administration was given for the second and subsequent administration”.
 
• If [1][2] described above is satisfied and the second and subsequent administrations are not given, the dosage should be aggregated as “160 mg, and no administration was given for the second and subsequent administration”.
 
• If the initial dose is 80 mg: the dosage is aggregated as “80 mg”.
 
• If the initial dose is 40 mg: the dosage is aggregated as “40 mg”.
 

Name of data	Derivation and calculation method
	
 
The dose is other than above, the dosage is aggregated as “Other”.
 

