Patients in whom dose increase was made	
Patients in whom 160 mg/2 weeks was administered as the initial dose, 80 mg/2 weeks as the second dose, 40 mg/2 weeks as the third and subsequent dose, and 160 mg or 80 mg was administered at least once thereafter are applicable.

Administration status (total number of administrations, dose)	
 
The number of administrations 
 
[1] Data should be sorted by the start date of the treatment, separate volume, and the number of the cycle of treatment described in “Administration status of this drug” in that order.
 
[2] Administration intervals should be calculated by administration status.
 
 
 
The administration interval should be 14 days for the initial and second administration.
 
The third and subsequent administration should be given according to following rules.
 
If there is a check mark in “once/2 weeks” box, the administration intervals should be 14 days, and in any other situations, a data should be obtained from “[HUMIRA BD] converted data to be provided for analysis”.
 
[3] The number of administrations by administration status should be calculated.
 
The number of administrations = (The last date of the administration (after complement) - the start date of the administration (after complement))/the administration intervals (days)
 
[4] Result obtained according to [3] is larger than 0 and smaller than 1, the number of administrations should be 1.
 
In addition, that number is 1 or larger, the number of administrations should be obtained by rounding off the decimal point.
 
[5] The number of administrations should be sum total of [4] by patients
 
 
Dose 
 
[1] If the dose of this drug is classified as other, the data should be obtained from “[HUMIRA BD] converted data to be provided for analysis”.
 
[2] The dose by administration status should be calculated.
 
 
 
The dose = The number of administrations × the dose
 
[3] Total dose should be sum total of [2] by patients
 
 
Mean daily dose 
 
Mean dose = Total dose/Total number of administrations
 
 
 
 

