Presence or absence of history of allergy	
If there is a check mark in a box for history of allergy in “patient information” in survey sheet, such patients are deemed to have allergy, and if there is a check mark in a box for “unknown about allergy”, whether patients have allergy is deemed as unknown, and if a column for “presence or absence of allergy” is not completed and in any other situations, patients are deemed to have no history of allergy.

Patients with hepatitis B viral infection	
Patients with description as “hepatitis→ viral” in “complication” and “Type B” in “hepatitis virus carrier” in “patient information”, are deemed to be patients with hepatitis B infection. In addition, patients have events corresponding to MedDRA PT code described in “161207 Hepatitis B (FIX) CRO” are deemed to have hepatitis B infection.

Presence or absence of smoking habit	
If there is a check mark in a box for presence or absence of smoking habit in the survey sheet, patients are deemed to have smoking habit. If there is a check mark in a box for absence of smoking habit in the survey sheet, patients are deemed to have no smoking habit. If there is a check mark in a box for unknown about smoking habit in the survey sheet, whether patients have smoking habit or not is deemed as unknown. If a column for “smoking habit” is not completed, whether patients have smoking habit or not is deemed as not described.

Patients in whom deviation from rules for administration of this drug is noted	
Patients who receive this drug at the dose other than “160 mg→80 mg→40 mg/2 weeks”, “only 160 mg”, or “160 mg→80 mg/2 weeks”, deviation is deemed to have occurred.

Presence or absence of self-administration	
If there is at least one check mark in a column for “Self-administration” in “Administration status” in the survey sheet, the patients are deemed to do self-administration. In any other situations, patients are deemed not to do self-administration.

Presence or absence of self-administration error	
If there is a check mark in a box for “self-administration error was present” in the survey sheet, self-administration error is deemed to be present, and if there is a check mark in a box for “self-administration error was absent”, self-administration is deemed to be absent.
 
In addition, regardless of presence or absence of check mark in

Name of data	Derivation and calculation method

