## 11. Method of dividing hierarchy of data

data	Method of dividing hierarchy
Dosage and administration	160mg→80mg→40mg/2 weeks, no changes thereafter 160mg→80mg→40mg/2 weeks, and 160mg or 80mg is administered at least once thereafter 160mg, and not administered thereafter 160mg→80mg, and not administered thereafter 80mg, and not administered thereafter 40mg, and not administered thereafter others
the number of administrations	at least once and less than 4 times at least 4 times and less than 12 times at least 12 times and less than 26 times at least 26 times and less than 39 times at least 39 times and less than 52 times at least 52 times and less than 65 times at least 65 times and less than 78 times at least 78 times
Total dose	lower than 500mg at least 500mg and lower than 1000mg at least 1000mg and lower than 2000mg, at least 2000mg and lower than 3000mg at least 3000mg unknown
Mean daily dose	lower than 40 mg at least 40 mg and lower than 60 mg at least 60 mg and lower than 80 mg at least 80 mg and lower than 100 mg at least 100 mg unknown

data	Method of dividing hierarchy
Administration duration	at least 0 week and shorter than 4 weeks (1-28 days) at least 4 week and shorter than 12 weeks (29-84 days) at least 12 weeks and shorter than 24 weeks (85-168 days) at least 24 weeks and shorter than 52 weeks (169-364 days) at least 52 weeks and shorter than 104 weeks (365-728 days) at least 104 week and shorter than 156 weeks (729-1093 days) unknown * When the start date of the administration is defined as 1
Reasons for discontinuation	Occurrence of adverse events, insufficient effect, patient's request, not visiting, others, multiple reasons, unknown, and not described
Sex	male, female, unknown, not described
Pregnancy/lactation	Without pregnancy/lactation, during pregnancy, during lactation, unknown, not described
Race	Japanese, other Asians, others, unknown, not described
Age (years)	Younger than 15 years, 15 years or older and younger than 65 years, 65 years or older, unknown/not described
Body weight (kg)	Lower than 30, 30 or higher and lower than 40, 40 or higher and lower than 50m, 50 or higher and lower than 60, 60 or higher, unknown/not described
Body height (cm)	Lower than 140, 140 or higher and lower than 150, 150 or higher and lower than 160, 160 or higher and lower than 170, 170 or higher and lower than 180, 180 or higher and lower than 190, 190 or higher, unknown/not described

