**“2.19.1 Treatment for patients who showed insufficient response to treatment”**

Patients included in analysis: In patients included in safety analysis, patients who discontinued the survey because of “insufficient effect” or patients in whom dose or the number of administration was adjusted because of “insufficient effect” should be

included.

Objective of analysis: Presence or absence of drugs used after discontinuation of this drug and distribution of the drugs used after discontinuation of this drug are shown.

Analysis items: The number of patients included in analysis should be calculated.

The number of patients and rate of these patients by “drugs used after discontinuation of this drug” and ”detailed classifications of drug used after the discontinuation of this drug“ defined in “11 method of dividing hierarchy for data” should be calculated.

Date of patients in whom dose or the number of administration was adjusted because of “insufficient effect” should be obtained from “[HUMIRA BD] converted data for provision for analysis”.

Notes: Detailed classifications of drug used after the discontinuation of this drug may be overlapped.

“2.19.2 Dosage and administration for patients who showed insufficient response to treatment”

Patients included in analysis: In patients included in safety analysis, patients who discontinued the survey because of “insufficient effect” or patients in whom dose or the number of administration was adjusted because of “insufficient effect” should be included.

Objective of analysis: Distribution of dosage and administration for patients who showed insufficient response to treatment is shown.

Analysis items: The number of patients included in analysis should be calculated.

The number of patients and rate of these patients to those included in analysis should be calculated by presence or absence of discontinuation and classification of dosage and administration (patients discontinued by the initial or second administration, patients who received this drug 3 times or more, the maximum dose for the third or subsequent administration is 40 mg/2 weeks, 40 mg/1 week, 80 mg/2 weeks, 80 mg/1 week, 160 mg/2 weeks, 160 mg/1 week, and others). Items with the number of 0, output by items should not be made.

Date of patients in whom dose or the number of administration was adjusted because of “insufficient effect” should be obtained from “[HUMIRA BD] converted data for provision for analysis”.

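### SAP Section 10.1 misassigns patients to dosage classes in three places and disagrees with Section 11, with limited effect on planned output

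*SAP*

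**What the plan says.** All places are in the SAP.

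- **Section 10.1, administration status (dosage and administration).** Steps [1] and [2] are a first dose of 160 mg and a second of 80 mg. Step [3] is "3] The third administration: Patients who receive this drug at the dose of 40 mg". Step [4], for the fourth and later entries, is "Patients whose survey sheet includes a check mark in “once per 2 weeks” box and a description of 40 mg as the dose". With no fourth entry, [1] to [3] are enough for the class of 160→80→40 mg every 2 weeks without change.
- **Same item, patients who stopped early.** One bullet begins "If [1][2] described above is satisfied and the second and subsequent administrations are not given, the dosage should be aggregated as" and then gives the 160 mg label already used by the bullet above it. Patients whose first dose is 80 mg or 40 mg are classed by that dose, whatever follows.
- **Section 11, dosage and administration.** After the 160 mg class, the list continues "160mg→80mg, and not administered thereafter 80mg, and not administered thereafter 40mg, and not administered thereafter others".
- **Section 10.1, deviation from the administration rules.** The flag applies to "Patients who receive this drug at the dose other than" three listed patterns: 160→80→40 mg every 2 weeks, 160 mg only, and 160→80 mg.
- **Section 10.1, dose increase.** After the 160, 80 and 40 mg sequence at 2-week intervals, patients in whom "160 mg or 80 mg was administered at least once thereafter are applicable".
- **Section 13.2, Table 2.19.2.** The regimens from the third administration on include "40 mg/2 weeks, 40 mg/1 week, 80 mg/2 weeks, 80 mg/1 week".

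**The concern.** A class label should assert only what its rule has checked, and the derivation section should be able to fill every class that the stratification section lists. Neither holds here. Step [3] leads to a label that states a 2-week interval without testing it. The bullet for patients with two doses contradicts itself. The 80 mg and 40 mg rules in 10.1 admit patients whom the Section 11 labels describe as having stopped.

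At stake is the description of how the drug was given in a survey that registers all treated patients. A programmer working from 10.1 and one working from Section 11 would put the same patient in different classes. The SAP also leaves open whether the deviation flag is built from the classes or from the recorded interval, and whether weekly dosing, which Table 2.19.2 foresees, has any place in the dose-increase flag.

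**Working it through.** The SAP gives no figure to reproduce. The check is a comparison of rules, followed by a short exposure calculation.

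**Can a third record run on at another interval?** Yes. The derivation of the last treatment date in 10.1 allows third and later records to be ticked as ongoing. For the number of administrations, 10.1 says "The third and subsequent administration should be given according to following rules": 14 days if the two-weekly box is ticked, otherwise an interval taken from a converted-data file. The interval is therefore available for the third record, and it need not be 14 days.

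**Eleven record patterns.** The middle column applies 10.1 as printed. The right column requires the 2-week interval on the third record and uses the Section 11 classes.

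| Pattern (mg) | 10.1 as printed | Interval checked, Section 11 classes |
|---|---|---|
| 160→80→40 two-weekly | unchanged | unchanged |
| 160→80→40 weekly, one open third record | **unchanged** | **other** |
| 160→80→40 two-weekly→40 two-weekly | unchanged | unchanged |
| 160→80→40 two-weekly→40 weekly | other | other |
| 160→80→40 weekly→40 two-weekly | **unchanged** | **other** |
| 160→80→40 two-weekly→80 | later 160 or 80 | later 160 or 80 |
| 160→80→40 weekly→80 | **later 160 or 80** | **other** |
| 160→80 only | **160 label** | **160→80** |
| 160 only | 160 | 160 |
| 80→40 two-weekly | **80** | **other** |
| 40→40 two-weekly | **40** | **other** |

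Six of the eleven rows change. The patterns were chosen to exercise the rules, so six of eleven is not a frequency.

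**The 160→80 row.** Step [2] means that a second dose of 80 mg was given, while the bullet also requires that no second dose was given. No patient meets both. Read by its apparent intent, the bullet sends these patients to the 160 mg label. Read literally, it catches nobody and they fall to the residual class. Either way the Section 11 class for 160→80 mg stays empty, although the deviation rule also lists that pattern separately.

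**Exposure to day 364.** Assume that the third record runs from start + 28 to start + 364 days, that weekly means 7 days, and that the first two doses count as one administration each.

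- Two-weekly: (364 − 28)/14 = 24 doses; 160 + 80 + 24 × 40 = 1200 mg in 26 administrations.
- Weekly: (364 − 28)/7 = 48 doses; 160 + 80 + 48 × 40 = 2160 mg in 50 administrations.
- Ratio of totals: 2160/1200 = 1.8.

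In Section 11, 26 and 50 administrations fall in different strata (26 to under 39, 39 to under 52), as do 1200 and 2160 mg (1000 to under 2000, 2000 to under 3000). Table 1.6 therefore separates the two regimens. The variable named mean daily dose does not: it is total dose over administrations, 1200/26 = 46.2 mg against 2160/50 = 43.2 mg, both in the stratum from 40 to under 60 mg.

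**The case against.** The strongest reply is that little depends on these classes, and most of it stands. No Section 13 output tabulates the Section 11 dosage classes. Listing 1.4 shows dates, days, initial and maximum dose and the two flags, but not the class. Table 2.3 takes only the maximum dose. The factor analyses in Tables 2.9 and 3.4 use neither the class nor either flag. The bullet for two doses looks like a copying slip, since Section 11 and the deviation rule both show the class that was meant.

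A reader might also infer more than the text supports:

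- **That the classification ignores the injection interval.** It does not. Step [4] checks it, so a weekly fourth or later record goes to the residual class. The gap is confined to the third record.
- **That the deviation flag misses weekly patients.** Its wording names the 2-week interval, and weekly dosing is other than that. It would miss them only if programmed from the 10.1 classes, which the SAP does not say.
- **That the dose-increase flag is wrong because weekly 40 mg never triggers it.** A flag for higher doses that counts higher doses matches its name and Section 11. Table 2.19.2 covers only patients with insufficient effect and also lists 40 mg every 2 weeks, so it does not contradict the flag. Counting a shorter interval would be a new rule. The SAP need only say whether it counts.
- **That the 1.8-fold difference is lost from the results.** Table 1.6 uses the recorded interval and captures it.

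The reply does not remove the three defects. Each is a stated derivation rule that assigns patients wrongly or cannot be applied.

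**Conclusion.** The dosage classification in Section 10.1 is wrong as written in three places: step [3] omits the interval that its class label asserts; the rule for 160→80 mg cannot be met and carries the wrong label; and the 80 mg and 40 mg rules do not match the Section 11 labels.

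Every patient with one of these patterns is affected, but how many there are is not in the document. No planned table tabulates the classes, and total exposure in Table 1.6 is unaffected. The visible output at risk is the pair of flags in listing 1.4, and the deviation flag only if it is built from the classes. This is worth correcting, with limited impact.

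The conclusion rests on reading each administration in the rule as one entry in the administration-status section of the survey sheet. That fits the sorting of entries by start date and the rule's reference to a description of a fourth administration. Which dosing rule is right is not judged here.

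**What to change.** Reconcile the dosage item in 10.1 with Section 11 and with the deviation rule:

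1. Apply to step [3] the same two-weekly box check that step [4] uses, so that the label states only what was tested.
2. Reword the bullet for [1] and [2] so that its condition is that the third and later administrations were not given, and give it the Section 11 label for 160→80 mg.
3. Make the 80 mg and 40 mg rules and labels agree: either require that no later record exists, or remove that restriction from the Section 11 labels.
4. State that the deviation flag is derived from the recorded interval as well as the dose.
5. Set the dose-increase flag beside the regimens in Table 2.19.2 and state whether a shorter interval counts. Either answer serves, provided that it is written down.

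The cost is SAP wording and reprogramming of the dosage class and, where needed, the two flags, all from data already collected. Some patients will move to the residual or 160→80 mg class, and the number flagged may change. No dosing rule is altered.

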### 9.3. Digits of the values displayed

Digits of the values displayed are as follows:

Types of values	Digits of values displayed
Mean value, standard deviation, and median value	Two digits subsequent to the valid digits for data are rounded off to display the value with valid digits plus 1 digits
The minimum value and maximum value	The number of digits of the value should be the same as that of valid digits of data.
The number of patients	The number should be displayed as integral number
Rate, 95% confidence interval	The second digit after the decimal point should be rounded off to display the value with 1 digit after the decimal point. However, when the value is displayed with 2 digits after the decimal point with the third digit after the decimal point being rounded off, such as the values in Appendix 2 or incidence of adverse events, rules of display should be based on layout of the tables and figures.
p value	The fifth digit after the decimal point should be rounded off to display the value with 4 digit after the decimal point. However, when the value is less than 0.0001, the value should be displayed as <0.0001
Valid number of digit	Disease duration should be displayed as the value with 1 digit after the decimal point. Valid number of digits for other data should be the displayed number of digits of the data

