	
identified, the date described as the last date of the treatment should be employed.
 
[3] When there is no description in the section for the last date of the third or subsequent treatment or there is a check mark in “Ongoing” box so that the last date of the treatment cannot be identified, following rules are applied.
 
 
● When the patients are included in the last period in the volume: The date should be complemented by the last follow-up date for relevant volume or a date obtained by subtracting 1 day from start date of the subsequent treatment, which is earlier.
 
● When the patients are included in not last period in the volume: The date should be complemented by a date obtained by subtracting 1 day from the start date of the subsequent treatment with this drug.
 
 
The last follow-up date should be defined as follows:
 
 
• The initial volume: Start date of the treatment with this drug + 364 days
 
• The second volume: Start date of the treatment with this drug + 728 days
 
• The second volume: Start date of the treatment with this drug + 1092 days
 
 
[4] When there is description in the section for the last date of the third or subsequent treatment but the date is incomplete so that the last date of the treatment cannot be identified, following rules are applied.
 
 
● When the date include year and month, but date is unknown: The date should be complemented by the last date of relevant month.
 
● When the date include year, but month and date is unknown: The date should be complemented by the last date in the last month of relevant year. In addition, when records in the subsequent treatment are created and the start date of the subsequent treatment is earlier than the complemented last date in the last month of the relevant year, the last date of the treatment should be complemented by the date obtained by subtracting 1 day from the start date of the subsequent treatment.
 
 
However, if description in the last date of the treatment in the records for which last date of the treatment was complemented according to above rules and there is a check mark in “Ongoing” box, following rules are applied:
 
 
● When the described last date of the treatment is later than the last date complemented according to above rules, the date complemented should be employed as the last date of the final treatment of this drug.
 
● When the described last date of the treatment is earlier than the last date complemented according to above rules, the date described should be employed as the last
 

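### The injection-count formula in SAP 10.1 counts the gaps between injections, so a third or later record closed by a written last-injection date comes out one injection short

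*SAP*

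**What the plan says.** All of the following is in SAP 10.1 unless another section is named.

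- **Count per record** (Administration status, step [3]): "The last date of the administration (after complement) - the start date of the administration (after complement))/the administration intervals (days"). For a two-weekly third or later record, "the administration intervals should be 14 days"; other intervals come from a converted data file.
- **Conversion to a whole number** (step [4]): a result that "is larger than 0 and smaller than 1, the number of administrations should be 1". For 1 or more, "the number of administrations should be obtained by rounding off the decimal point". A result of exactly 0 is not mentioned.
- **Closing date of a third or later record** (The last date of the final treatment, [2] and [3]): with a complete written date and the Ongoing box unticked, "the date described as the last date of the treatment should be employed". With no date, or Ongoing ticked, and a record that is not the last in its volume: "The date should be complemented by a date obtained by subtracting 1 day from the start date of the subsequent treatment with this drug". For the last record in a volume, the closing date is the earlier of that day and the last follow-up date (start + 364, 728 or 1092 days).
- **Use of the result**: total dose is count times dose, and mean dose is total dose divided by count. These feed Table 1.6 with the bands of Section 11 (the lowest count band is "at least once and less than 4 times") and the mean-dose and duration fields of listing 2.3. Mean daily dose is also a tested factor in Tables 2.9 and 3.4.

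**The concern.** Elapsed days divided by the interval give the number of intervals. That equals the number of injections only if the closing date marks the end of the last interval. The day before the next start does so, to within a day. A written date that is itself an injection day does not: it falls one interval earlier. The SAP puts both kinds of date into the same formula, so identical injections can be counted differently according to how the form was completed. The days-on-treatment derivation in the same section does add 1, but the injection count does not.

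At stake are the exposure figures in Table 1.6 and the patient listing. Short treatments are the most affected, because one injection is a larger share of their total.

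**Working it through.** The SAP gives no worked count, so there is no figure to reproduce. The check applies its rules to k injections, evenly spaced 14 days apart, in one third-or-later record.

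**Closure by written date (taken as the day of the last injection).** Last - start = 14(k-1), so the quotient is k-1.

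**Closure the day before the next start.** Last - start = 14k-1, so the quotient is k - 1/14.

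| k | Written date: quotient, count | Next start - 1: quotient, count |
|---|---|---|
| 1 | 0, not covered by step [4] | 0.93, 1 |
| 2 | 1, 1 | 1.93, 2 |
| 3 | 2, 2 | 2.93, 3 |
| 6 | 5, 5 | 5.93, 6 |
| 24 | 23, 23 | 23.93, 24 |
| 76 | 75, 75 | 75.93, 76 |

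Taking the uncovered zero as 0, the gap is exactly 1 for every k from 1 to 79. It is also 1 at each k tried with a 7-day interval, and for k = 2, 6 and 24 when the closing date moves by up to 6 days either way. From k = 2 on, the quotient is at least 1, so repairing the uncovered zero case does not repair the shortfall.

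**By dates.** Injections on days 29, 43, 57, 71 and 85: a written end on day 85 gives (85-29)/14 = 4. A blank end with the next record starting on day 99 gives (98-29)/14 = 4.93, counted as 5.

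**Rounding.** The table reads rounding off as nearest, the sense it has in Section 9.3 ("The second digit after the decimal point should be rounded off to display the value with 1 digit after the decimal point"). Under truncation both closures give k-1 for k of 2 or more: the difference between them goes, but the written-date record is still one short.

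**Closure at the last follow-up date.** With the third dose at start + 28, the quotients are (364-28)/14 = 24, (728-28)/14 = 50 and (1092-28)/14 = 76. On schedule there are 24, 50 and 76 injections in the record if the one due on the follow-up date is not counted, and 25, 51 and 77 if it is.

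**Effect on the Section 11 bands.** Assume 160 mg, 80 mg, then 40 mg doses, the first two counted as 1 each, and all later injections in one dated record. Let n be the true total, 4 or more.

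- Count: n-1 instead of n. The band changes only at n = 4, 12, 26, 39, 52, 65 or 78.
- Total dose: 40n + 120 instead of 40n + 160. The cut-points 500, 1000, 2000 and 3000 mg are crossed only at n = 9, 21, 46 and 71.
- Mean dose: 40 + 160/(n-1) instead of 40 + 160/n. The band changes only at n = 5 (72.0 becomes 80.0) and n = 9 (57.8 becomes 60.0).

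Examples:

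- n = 4: count 3, total 280 instead of 320 mg, mean 93.3 instead of 80.0 mg. The count band changes; the mean stays in the 80 to below 100 mg band.
- n = 9: count 8, total 480 instead of 520 mg, mean 60.0 instead of 57.8 mg. The total-dose and mean-dose bands both change.
- n = 26: count 25, total 1160 instead of 1200 mg, mean 46.4 instead of 46.2 mg. Only the count band changes.

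A patient with several dated records of two or more injections loses one injection in each.

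**The case against.** The strongest reply is that the SAP never defines the written last date as an injection day. The record has a start date and an Ongoing box, and a site could write the day on which a regimen period ended. The present formula is then right. This stands as a limit on the finding. The opposite reading has support: the single first and second doses are given a last date equal to their start date, and the formula itself speaks of the last date of administration. That is support, not proof.

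A reader might also infer that the shortfall biases exposure by discontinuation, since patients who stop have a written date and continuing patients are closed by a cut-off. The SAP does not support going that far. It does not say who has written dates, and a change of regimen can produce one too. Continuing patients closed at the last follow-up date may themselves be one short: the record-exclusion rule drops only records starting after that date, so an injection on the day itself lies inside follow-up.

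The effect on mean dose is small, and the SAP gives no basis for saying that the tests in Tables 2.9 and 3.4 would change. The 4-injection example also depends on record layout. If the third and fourth injections are separate records, a dated fourth falls into the uncovered zero case, and setting that to 1 gives the right total. What remains is that two legitimate closing dates for the same injections give different counts under the SAP's own rounding, and that a dated last injection is one short under either rounding.

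**Conclusion.** The point holds in a limited form. Where the written last date is the last injection day, the SAP's rule counts k injections as k-1 in each such third-or-later record of two or more injections. The disagreement with records closed the day before the next start also needs nearest rounding; the undercount itself does not. The size is one injection per dated record, 40 mg at a 40 mg dose, with band changes confined to totals next to a cut-point. The number of patients affected cannot be known from the SAP. An association with discontinuation is plausible but unproven. This is a fault in descriptive exposure tables, worth correcting because the rule is wrong as written and cheap to repair.

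**What to change.** Replace steps [3] and [4] with one rule for every closure: number of administrations = integer part of (last date - start date)/interval, plus 1. On a regular schedule:

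- written last-injection date: integer part of k-1, plus 1 = k;
- day before the next start, or a written interval end on that day: integer part of k - 1/14, plus 1 = k;
- zero quotient: 0 + 1 = 1, which also settles the first and second doses.

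State whether an injection on the last follow-up date itself is counted. The rule gives 24 + 1 = 25 for a first-volume record, which counts it. If it is not to be counted, end those records one day earlier: (363-28)/14 = 23.93, integer part 23, plus 1 = 24.

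The cost is a short text change and the matching program line, with no new data. The rule is less tolerant of irregular timing: a dated last injection given a day or more early is undercounted by one, and a next record starting a day or more late adds one to the record before it. If written dates are confirmed to be injection days, use the rounded quotient plus 1 for those records instead; next-start closures can then keep the present rounded quotient, which absorbs shifts of up to 6 days. Without that confirmation, rounding and adding 1 is unsafe: a written interval end on day 98 would give (98-29)/14 + 1 = 5.93, counted as 6 for 5 injections.
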